#### 5.3.3. Handling of Withdrawals and Discontinuation of Administration

Subjects who discontinue will be asked about the reason(s) for their discontinuation and about the presence of any AEs. If possible, they will be seen and assessed by an investigator(s). AEs will be followed to resolution and/or until deemed stabilized by the investigator. Subjects who discontinue may be subject to replacement as described in Section 5.3.4. If subjects are not evaluable and thus are replaced, their samples will be discarded. If the subject received any amount of study drug, they will be encouraged to follow up for safety.

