#### 5.3.2. Reasons for Withdrawal and Discontinuation of Study Product Administration

Subjects may voluntarily withdraw their consent for study participation at any time without penalty or loss of benefits to which they are otherwise entitled.

An investigator may also withdraw a subject from receiving the study drug for any reason. Follow-up safety evaluations will be conducted, if the subject agrees. If a subject withdraws or is withdrawn before completion of the study, the reason for this decision will be recorded in the eCRF. The reasons might include, but are not limited to the following:

- Subject no longer meets eligibility criteria
- Subject becomes noncompliant

- Subjects develops a medical disease or condition, or new clinical finding(s), for which continued participation, in the opinion of the investigator, might compromise the safety of the subject, interfere with the subject's successful completion of this study, or interfere with the evaluation of responses
- Subject is lost to follow-up
- Subject becomes pregnant

The investigator will be explicit regarding study follow-up (e.g., safety follow-up) that might be carried out despite the fact the subject will not receive further study drug. If the subject consents, every attempt will be made to follow all AEs through resolution. The procedures that collect safety data for the purposes of research will be included in the original ICF or the investigator may seek subsequent informed consent using an IRB/IEC-approved ICF with the revised procedures.

The investigator will inform the subject that data already collected will be retained and analyzed even if the subject withdraws from the trial.

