#### 5.3.4. Subject Replacement

Subjects who initiate the Treatment Phase but are not evaluable will be replaced.

An evaluable subject is defined as a subject who receives all doses of ZTI-01, undergoes BAL at the randomized sampling timepoint with BAL return volume adequate for testing, and undergoes at least the one blood sampling timepoint that is concurrent with the assigned BAL sampling timepoint, with blood sampling volume that is adequate for testing. Replacement subjects will undergo study procedures on a separate date.

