#### DMID/NIAID/NIH

#### CONFIDENTIAL

- Obtain PK blood samples at 15 timepoints: before (within 10 minutes) the first, second, and third doses of study drug, at 30 minutes (during infusion), 1 hour (within 5 minutes after the end of infusion), 1 hour 15 minutes, 2, and 5 hours from the start time of the first infusion of ZTI-01, and at 30 minutes (during infusion), 1 hour (within 5 minutes after the end of infusion), 1 hour 15 minutes, 2, 5, 8, and 12 hours from the start time of the third (last) infusion of ZTI-01
- Measurement of sodium, potassium, magnesium, calcium, and phosphorus approximately 2 hours prior to the assigned bronchoscopy timepoint
- A standardized bronchoscopy with BAL sampling will be performed at single timepoint based on each subject's schedule assignment at either 30 minutes, 1 hour 15 minutes, 2, 5, or 8 hours after the start time of the third (last) infusion of ZTI-01
- Collect a blood sample to measure serum urea concentration just before or during bronchoscopy

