#### 8.2.2. Bronchoscopy and Bronchoalveolar Lavage (BAL)

Each subject will be assigned to one bronchoscopy sampling timepoint. The bronchoscopy sampling times will be at 30 minutes, 1 hour 15 minutes, 2, 5, and 8 hours from the start time of the third (last) infusion of ZTI-01. A total of 6 subjects will be assigned to each of the five BAL sampling times.

Sodium, potassium, magnesium, calcium, and phosphorus will be measured approximately 2 hours prior to each subject's bronchoscopy timepoint. Subjects with grade 2 or higher abnormalities (Appendix B) in these electrolytes will not receive any further study product and will not undergo bronchoscopy.

Bronchoscopy will be performed in a standardized fashion according to the MOP. Topical lidocaine will be applied to the upper airways to prepare subjects for bronchoscopy. If needed, 1.0% percent lidocaine

CONFIDENTIAL

DMID Protocol 16-0058	Version 9.0
IV Fosfomycin PK Study	27 August 2020

will be used in the lower airway. A fiberoptic bronchoscope will be inserted into the right middle lobe. Four 50-mL aliquots of sterile normal saline will be instilled into the right middle lobe and each specimen will be immediately aspirated and placed on ice. BAL samples for PK measures will be obtained  $\pm 15$  minutes from the subject's assigned sampling time. The start and stop times of BAL will be recorded on the eCRF.

Subjects will be continuously monitored during bronchoscopy. Blood pressure, heart rate, respiratory rate, and peripheral oxygen saturation will be recorded before and at the end of bronchoscopy. Subjects will undergo cardiac monitoring during bronchoscopy.

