# 9.5. Halting Rules

If any of the halting rules, as outlined below, is met, further enrollment and dosing will be withheld until the SMC reviews the safety data and provides its recommendations.

- Two subjects experience any related Grade 3 systemic AE
- Two subjects experience the same related Grade 3 laboratory AE (per Medical Dictionary for Regulatory Activities High Level Group Term)
- One subject experiences a related SAE

A decision to reinitiate the trial and proceed with study drug administration will be made by DMID based on the recommendation of the SMC.

If the following individual halting rule is met, the individual will not undergo further dosing or study procedures.

• Subject experiences a grade 2 or higher abnormality in sodium, potassium, magnesium, calcium, or phosphorus, when checked approximately 2 hours prior to the bronchoscopy timepoint

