# Table 8: Probability of observing at least one event for a range of true event rates based on a sample size of n=30 subjects

## 11.3. Final Analysis Plan

#### Analysis Populations:

All subjects who receive any amount of ZTI-01 will be included in the safety population. The pharmacokinetic analyses will be performed using the population of evaluable subjects. An evaluable subject is defined as a subject who receives all doses of ZTI-01, undergoes BAL at the randomized sampling timepoint with BAL return volume adequate for testing, and undergoes at least the one blood sampling timepoint that is concurrent with the BAL sampling timepoint, with blood sampling volume that is adequate for testing.

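### Samples from replaced subjects are discarded and all plasma PK is confined to subjects with an evaluable BAL, so valid plasma profiles are lost for good

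*Protocol*

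**What the plan says.** Protocol 5.3.3 states: "If subjects are not evaluable and thus are replaced, their samples will be discarded". Section 5.3.4 fixes how far that reaches: "Subjects who initiate the Treatment Phase but are not evaluable will be replaced". Together they cover every dosed subject who turns out not to be evaluable.

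On the analysis side, Protocol 11.3 says "The pharmacokinetic analyses will be performed using the population of evaluable subjects", and SAP 6.3.2 and 10.1 repeat this. Evaluability needs all three doses, one blood sample concurrent with the BAL, and that the subject "undergoes BAL at the randomized sampling timepoint with BAL return volume adequate for testing". Neither document defines a separate plasma population.

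Subjects with a Grade 2 or higher abnormality "in these electrolytes will not receive any further study product and will not undergo bronchoscopy" (Protocol 8.2.2). The individual halting rule in 9.5 adds that "the individual will not undergo further dosing or study procedures". The check is made "approximately 2 hours prior to the assigned bronchoscopy timepoint" (Protocol 7.3). A stopped subject has no BAL and so cannot be evaluable.

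Two other places point towards keeping what was collected. Protocol 5.3.2 says "The investigator will inform the subject that data already collected will be retained and analyzed even if the subject withdraws from the trial". SAP 10.2 plans to attempt all scheduled blood draws whatever amount of drug was given.

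**The concern.** Plasma PK is a stated objective alongside intrapulmonary PK (Protocol 3.1). The evaluability definition suits ELF and AM penetration, where plasma and lavage must be matched, but it does not suit plasma noncompartmental analysis. A subject with all 15 plasma samples and a poor lavage return is excluded and the samples destroyed. A subject with one plasma sample at the right time and a good lavage qualifies. Dose 1 Cmax, Tmax and AUC0-8 (SAP 10.4.1, Table 37) need neither a BAL nor Dose 3.

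The electrolyte-stopped subjects matter most. Protocol 2.3.1 lists hypokalemia, hypocalcemia and hypophosphatemia as common with this drug. These subjects stay in the safety population, but no exposure data would remain to set beside their events, although the safety monitoring committee is to review safety and PK data at the end of enrollment (Protocol 9.6.2). SAP 7.2 and 10.1 also treat exclusion from PK as a decision made on review of deviations, and disposal pre-empts that review. An exclusion can be reversed in a sensitivity analysis; a discarded, unassayed sample cannot be recovered.

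**Working it through.** **Samples per subject** (Protocol 7.3, Table 3). Around Dose 1: 6. Before Dose 2: 1. Around Dose 3: 8. Total 6 + 1 + 8 = 15. SAP 4.5.2 reports the pre-Dose 2 sample as the 8-hour point of Dose 1, so the Dose 1 profile has 6 + 1 = 7 samples.

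**BAL failure.** All 15 samples can exist, giving full Dose 1 and Dose 3 profiles. If only the concurrent blood sample is missing, 15 − 1 = 14 can exist.

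**Electrolyte stop.** The check falls at the BAL time minus 2 h. The counts assume that draws end at the stop, as 9.5 implies.

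| BAL group | Check, relative to Dose 3 start | Dose 1 samples | Dose 3 samples already drawn | Total |
|---|---|---|---|---|
| 0.5 h | −1.5 h | 7 | 0 | 7 |
| 1.25 h | −0.75 h | 7 | 0 | 7 |
| 2 h | 0 h | 7 | 1 (pre-dose) | 8 |
| 5 h | +3 h | 7 | 5 (to 2 h) | 12 |
| 8 h | +6 h | 7 | 6 (to 5 h) | 13 |

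Dose 1 Cmax, Tmax and AUC0-8 can be estimated in every group. Dose 3 Cmax and Tmax, and the Cmax accumulation ratio, can be estimated in the 5 h and 8 h groups. Observed Dose 3 AUC0-8 can be estimated in none.

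**How many stops.** Table 8, the only computed figure in the sample-size section, is 1 − (1 − p)^30. It reproduces at all eight rates; for example p = 1%, 5% and 10% give 26.03%, 78.54% and 95.76% against the printed 26%, 79% and 96%. The documents give no Grade 2 or higher electrolyte rate. If it were 1%, 5% or 10% (assumed), the expected stops among 30 dosed subjects would be 0.3, 1.5 and 3.0, and the chance of at least one would be those same Table 8 values.

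**Precision.** The standard error of a log-scale mean scales as 1/√n. With 40 subjects instead of 30, √(30/40) = 0.87. With the SAP's 36, √(30/36) = 0.91. The 95% interval factor for a geometric mean is exp(t × s/√n), with s = √ln(1 + CV²) and t the 97.5% point on n − 1 degrees of freedom. The documents give no CV, so these are assumed:

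- CV 20%: 1.077 (n = 30) to 1.065 (n = 40)
- CV 30%: 1.116 to 1.098
- CV 40%: 1.155 to 1.131

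**Selection.** Simulation: draw 30 + k subjects, give each a stop risk with an assumed correlation with log exposure, drop the k at highest risk, and compare the geometric mean of the remaining 30 with the truth. At correlation 0 the bias is 0. At correlations 0.5 to 1 with k = 3, it is −1.7% to −3.4% (CV 20%), −2.4% to −4.9% (CV 30%) and −3.3% to −6.4% (CV 40%). With k = 5 and CV 30% it is −3.7% to −7.2%. These figures show only what such a link would do; a negative correlation would reverse the sign.

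**The case against.** The case against has real force on several points.

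- A reader might infer that 5.3.3 flatly contradicts 5.3.2. It need not: 5.3.2 concerns data already collected when a subject withdraws, whereas 5.3.3 concerns samples. Unassayed plasma is not yet data, and a low lavage return is not a withdrawal. What remains is a tension worth removing.
- A reader might multiply 10 alternates by 15 samples and conclude that 150 samples are lost. The documents do not support that. Under Protocol 5.3.1 alternates also take the place of subjects who do not present or who fail eligibility on admission, and those subjects were never dosed. Electrolyte-stopped subjects have 7 to 13 samples if draws end. The 0.87 ratio shares the same ceiling, and the 0.91 ratio uses a SAP count written against protocol version 6.0, not the current 9.0.
- Replacement still targets 30 evaluable subjects, so the planned precision is not undermined.
- Protocol 3.2 places the plasma parameters after the third dose, and SAP 10.4.1 reports half-life, clearance and volume for Dose 3 only. If draws end at a stop, those parameters and the AUC accumulation ratio remain conditioned on not being stopped whatever happens to the samples. Keeping the samples of stopped subjects recovers mainly Dose 1.
- The trial tests no hypothesis, and one matched population is coherent for a penetration study.

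All of this limits the size of the point. None of it gives a reason to destroy plasma from a fully dosed subject whose lavage failed, or a complete Dose 1 profile.

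**Conclusion.** The point holds as a cheap improvement, not as a flaw that invalidates the analysis. The loss of valid plasma profiles follows directly from the text and is irreversible. It is complete for BAL failures (up to 15 samples) and confined to Dose 1 plus part of Dose 3 for electrolyte stops, provided draws end under 9.5. If draws continued under SAP 10.2, more would be lost.

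Dose 1 plasma summaries are conditioned on not having a possible drug effect. A reader might go further and infer that they understate exposure because the stopped subjects had high concentrations. The documents do not support that. Protocol 2.3.1 links hypokalemia to sodium load, and 6.2 gives the same 1980 mg of sodium with each dose to everyone. Nothing states that stopped subjects would have higher fosfomycin concentrations. Stops may also be few: electrolytes must be normal at entry (exclusion criterion 25, footnote 12), and laboratory abnormalities in the earlier single-dose healthy-volunteer study were mild. The size and direction of any bias cannot be determined, and the simulated figures rest on assumed correlations and CVs.

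The reasons to act are irreversibility and selective exclusion; the gain in precision is minor.

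**What to change.** 1. Delete the discard sentence in Protocol 5.3.3. Retain and assay plasma from dosed subjects, subject to their consent.
2. In Protocol 11.3 and SAP 6.3, define a plasma PK population by dose: dosed subjects with samples sufficient for the parameter. Dose 1 parameters need only Dose 1; comparisons between doses need both. Use it for SAP Tables 35–40.
3. Keep the BAL-evaluable population for Tables 41–43, including the plasma AUC0-8 denominator in SAP 10.3.2, so that penetration stays matched.
4. Show Tables 37 and 38 in both populations.
5. Reconcile Protocol 9.5 with SAP 10.2 on whether blood draws continue after a subject is stopped. This takes no view on the stopping rule itself.

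The cost is a short protocol and SAP amendment and the assay of plasma already drawn, for which 150 samples is a ceiling unlikely to be approached. Items 1 to 4 need no new draws or visits, and the target of 30 evaluable subjects is unchanged. Protocol 14.8 already provides storage for up to 189 days, so the extra assays would need to fit within that limit.

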#### 5.3.4. Subject Replacement

Subjects who initiate the Treatment Phase but are not evaluable will be replaced.

An evaluable subject is defined as a subject who receives all doses of ZTI-01, undergoes BAL at the randomized sampling timepoint with BAL return volume adequate for testing, and undergoes at least the one blood sampling timepoint that is concurrent with the assigned BAL sampling timepoint, with blood sampling volume that is adequate for testing. Replacement subjects will undergo study procedures on a separate date.

#### 5.3.5. Termination of Study

The trial may be terminated at any time at the discretion of the Sponsor, DMID. Other possible reasons for study termination include development of significant laboratory toxicities outside of those AEs characterized in the label and/or literature for the study drug. If the trial is prematurely terminated by the Sponsor, any regulatory authority, or the investigator for any reason, the investigator will promptly inform the study subjects and assure appropriate therapy or follow-up for the subjects, as necessary. The investigator will provide a detailed written explanation of the termination to the IRB/IEC.

DMID/NIAID/NIH

# 6. STUDY INTERVENTION/INVESTIGATIONAL PRODUCT

## 6.1. Study Product Description

#### 6.1.1. Acquisition

The non-US commercial drug product that will be used in the trial is a single vial of ZTI-01 disodium powder (4 g presentations with recrystallized succinic acid, in a Type 1 glass vials). Nabriva Therapeutics Inc. will provide DMID an adequate amount of ZTI-01 to support the trial, and will ship it to the following address at Fisher BioServices for storage and site distribution:

#### E-mail: [contact]

Sterile water for injection (WFI) will be the diluent and will be supplied by DMID through Fisher BioServices.

Study product will be shipped to DEPRU upon request and approval by NIAID.

#### 6.1.2. Formulation, Packaging, and Labeling

#### ZTI-01

Each Type 1, glass vial of ZTI-01 contains sterile white powder consisting of 5.28 g of fosfomycin disodium (equivalent to 4 g of fosfomycin and 1.28 g of sodium) and the inactive ingredient: recrystallized succinic acid. Each gram of ZTI-01 contains 330 mg of sodium.

Vials will be labeled with protocol number, product identity -4 g of ZTI-01 (fosfomycin for injection), lot number, expiry date, and the IND caution statement "New Drug – Limited by Federal Law to Investigational Use Only," a statement to store at controlled room temperature, and a statement that each vial is for intravenous, single use only.

WFI

DMID/NIAID/NIH

CONFIDENTIAL

The WFI, United States Pharmacopeia (USP) is nonpyrogenic and contains no bacteriostatic, antimicrobial agent, or added buffer. This product will be used to dilute the ZTI-01 and will be supplied as a single-dose vial.

## 6.1.3. Product Storage and Stability

Glass vials of ZTI-01 will be stored in a secure and locked research pharmacy, with limited access and available to appropriate study personnel only, at controlled room temperature of 20°C to 25°C (68°F to 77°F). If a temperature excursion outside of 15°C to 30°C (59°F to 86°F) occurs, the site will discontinue use of the vial(s) and notify the DMID Product Support Team (PST) and Nabriva within 24 hours of awareness of the excursion, according to the MOP.

The Investigator, or a designee (e.g., research pharmacist) will ensure that all study drugs are appropriately stored and in accordance with applicable regulatory requirements.

Sterile water for injection (WFI) will be stored at USP controlled room temperature 20°C to 25°C (68°F to 77°F).

# 6.2. Dosage, Preparation, and Administration of Study Drug

Preparation of ZTI-01 for IV infusion will be performed by DEPRU's Research Pharmacist according to the protocol-specific MOP. The procedure for reconstituting the vials with sterile water for injection (WFI) is presented in Table 5.

ZTI-01 (fosfomycin) dosage	Number of vials reconstituted with 20 mL of sterile WFI added to each vial	Volume of Sterile WFI to dissolve ZTI-01 powder	Volume of dissolved ZTI- 01 to be added for infusion	Volume of WFI to be added for infusion	Total volume for infusion
6 g	2	40 mL (20 mL for each of two vials)	30 mL (15 mL from each of two vials)	170 mL	200 mL

#### Table 5: ZTI-01 dose preparation guidelines

Each 1 g dose of ZTI-01 contains 330 mg of sodium. Due to the salt load of the formulation, sterile WFI will be used to reconstitute each ZTI-01 vial and to prepare the 200 ml ZTI-01 infusion (Table 6).

A total of two 4 g vials are required to prepare the 6 g dose. Deliver 20 mL of sterile WFI from the syringe into each vial containing 4 g of ZTI-01 powder to dissolve the powder. Always use sterile WFI and aseptic technique to reconstitute the powder. A slight degree of warming occurs when the powder is dissolved upon reconstitution of the vial, due to an exothermic reaction. After reconstitution, the product

```
DMID/NIAID/NIH
```

DMID Protocol 16-0058	Version 9.0
IV Fosfomycin PK Study	27 August 2020

will be used to prepare the infusion solution as follows, and as further detailed in the MOP: Using aseptic technique, withdraw an equal amount (15 mL) from each reconstituted vial (a total volume of 30 mL from both vials). The solution that is left in each vial will remain "unused." Add the 30 mL of diluted ZTI-01 to 170 mL of sterile WFI to yield the 200 mL total volume for infusion. The storage for the infusion bag, before administration, is limited to 4 hours at room temperature (20-25°C) or 24 hours at refrigerated conditions (2 - 8°C).

	Table 6: ZTI-01	(disodium	fosfomycin	) reconstitution	with	WFI
--	-----------------	-----------	------------	------------------	------	-----

Dose	Preparation Steps
	Step 1: Add 20 mL of sterile WFI to each of two vials of ZTI-01 powder
6 g	Step 2: Draw 30 mL total from both vials of diluted ZTI-01. Note: Draw an equal amount (15 mL) from each dissolved vial; the 5 mL left in the vials remain "unused."
	Step 3: Add the 30 mL of dissolved ZTI-01 to 170 mL of sterile WFI to yield the 200 mL total volume for infusion.

Note: The pharmacy will need to use/reconstitute 2 vials for each 6 g dose.

ZTI-01 should always be administered as a 200 mL infusion over 1 hour (+10 minute window).

Note: Each 1 g dose of ZTI-01 contains 330 mg of sodium; a 6 g dose of ZTI-01 contains 1980 mg of sodium. Each subject receiving 3 doses per protocol will be administered 5940 mg of sodium.

The ZTI-01 6 g infusion solution will be infused intravenously over 1 hour (+10 minute window) using an IV infusion pump at a rate set to 200 mL/hr. A dose will be administered every 8 hours for 3 doses.

Administering sterile WFI alone (i.e., with no additives) may increase risk of hemolysis in some subjects due to hypotonicity. Although the IV infusion of sterile WFI alone is contraindicated, the addition of ZTI-01 to sterile WFI is appropriate and recommended for IV administration. The use of 0.9% NaCl (isotonic saline) for infusion with ZTI-01 will be avoided, as the resultant hyperosmolar solution may irritate the vein.

# 6.3. Modification of Study Drug for a Subject

None

DMID/NIAID/NIH

CONFIDENTIAL

### 6.4. Accountability Procedures for the Study Drug

Chain of custody will be documented between the on-site pharmacy and the clinical staff responsible for administering the study drug.

The Site Principal Investigator (PI) is responsible for the distribution and disposition of the study drug, and has ultimate responsibility for accountability. The PI may delegate to the Site Research Pharmacist responsibility for study drug accountability. The Research Pharmacist will be responsible for and will maintain and document logs of receipt, accountability, dispensation, storage conditions, and final disposition of study drug. Upon completion or termination of the trial, all unused and used vials of ZTI-01 will be disposed according to DEPRU's standard operating procedures (SOPs) after accountability. The investigator is responsible for ensuring that no study drug is disposed until it is fully accounted for by the monitor.

